Effects of Isotretinoin on CYP2D6 Activity

NCT03076021

3/6/2017

Background:

CYP2D6 is a key drug metabolizing enzyme responsible for the metabolism of ~25% of all drugs eliminated by the cytochrome P450 system, including clinically important drugs such as antiarrhythmics, opioids, cough suppressants, antidepressants, antipsychotics, antihypertensives, and antihistamines. As such, understanding CYP2D6 regulation in humans is critical not only for special populations, but also more broadly for patients in general. This study will be the first step towards gaining insight into possible endogenous biomarkers of CYP2D6 regulation and activity in humans, thus moving us closer to individualized drug dosing. In the general population, many of these drugs have been titrated to clinical response, but there has been a desire to individualize therapy. Even after accounting for genotype, CYP2D6 activity varies 4- to 30-fold in extensive metabolizers. If our hypothesis proves to be true, we will continue research in this area, with the goal of developing one or more useful biomarkers to be used in conjunction with genotype to help guide dosing of CYP2D6-metabolized drugs.

Based on *in vitro* and animal studies as well as preliminary human data, **we hypothesize that retinoic acid concentrations and retinoid signaling in the liver regulates CYP2D6 expression and activity in humans, which in turn contributes to inter-individual pharmacokinetic variability of CYP2D6 substrates**. This study will directly test our hypothesis by evaluating CYP2D6 activity prior to and in the presence of concomitant 13-cis-retinoic acid (isotretinoin) in adolescent patients. Higher retinoic acid concentrations should lead to lower CYP2D6 activity. This much needed work will provide foundational mechanistic understanding and translate new basic science research findings into humans. The administration of all-trans-retinoic acid down regulates CYP2D6 in the humanized mouse model. The sum of the data regarding retinoid regulation of CYP2D6 from *in vitro* studies and animal models leads us to believe that administration of retinoic acid will lead to decreased CYP2D6 transcription, expression and activity. Since animal models are not always predictive of the effects in humans, it is now time to translate this work into humans.

In non-pregnant adolescents, there is more than 2-fold variation in retinol concentrations. **Isotretinoin has been a commonly used medication in adolescent patients for decades as it is uniquely effective at improving severe acne.** However, we are unable to locate any published studies evaluating the effects of isotretinoin on CYP2D6 activity in humans. Some degree of acne affects almost all adolescents 15-17 years of age, with approximately 15–20% of teenagers developing moderate to severe acne. In 2000, approximately 2 million prescriptions were written for isotretinoin in the United States. If our hypothesis holds true, given the frequency of isotretinoin use in the adolescent population and the potential for interaction with CYP2D6 substrates, it is essential that we evaluate isotretinoin's effect on CYP2D6 activity and simultaneously directly test the hypothesis that retinoids play a role in CYP2D6 regulation in humans. **The therapeutic administration of isotretinoin provides us with a unique opportunity to directly explore the mechanism of CYP2D6 regulation by retinoic acid in humans.**

[figure not shown]
In summary, adolescent patients commonly experience medical conditions that require treatment with CYP2D6 substrates. Although genetics play an important role in CYP2D6 variability, even after accounting for genetic variation, there is still a great deal of unaccounted variability in CYP2D6 activity. High variability makes the utilization of CYP2D6 substrates challenging in this special population. With strong basic science data suggesting that retinoids play a key role in regulation of CYP2D6, exploring the relationship between CYP2D6 activity and retinoid concentrations in humans will provide mechanistic understanding of the variability in drug therapy, which is critical to the provision of individualized pharmacotherapy and the first step toward development of an endogenous biomarker that potentially could be used in combination with genetics to predict CYP2D6 activity.

Objective:

To investigate if isotretinoin (13-cis-retinoic acid) administration decreases CYP2D6 activity in adolescent patients

Design:

Routinely at the UW Dermatology clinic, female patients with severe cystic acne who will be receiving isotretinoin undergo an initial evaluation, which includes laboratory tests (including a pregnancy test). Thirty days later, the pregnancy test is repeated and isotretinoin is initiated at 0.5 mg/kg/day. Twenty-eight days later, the pregnancy and laboratory tests are repeated and isotretinoin is increased to 1 mg/kg/day and continued for 3-4 months. Pregnancy and laboratory tests are repeated every 28 days. A similar protocol is followed for the male patients, excluding the pregnancy tests. The timing of our proposed study will fit into routine clinical visits and enhance the ease and success of study conduct.

Study Design

This is a prospective, pharmacokinetic study of oral dextromethorphan in adolescent patients. The study will be divided into 2 phases. Phase 1 will occur prior to initiation of isotretinoin and involve a single dose of oral dextromethorphan. Phase 2 will occur ≥ 1 week after initiation of steady-state isotretinoin and will repeat the single oral dose of dextromethorphan. Each subject will serve as his or her own control. All studies will be performed at the University of Washington.

Experimental Methods:

4.3.3. Study Design Summary:

Test	Phase 1 Pre-isotretinoin	Phase 2 Concomitant Isotretinoin
CYP2D6 genotype (pre-DM study)	X	

Dextromethorphan single 30 mg oral dose	X	X
Concomitant steady state isotretinoin administration		X
4-hour urinary DM/DX MR	X	X
Total plasma all-trans retinoic acid, 13-cis-retinoic acid, retinol (all-trans and 13-cis), retinyl palmitate, 4-oxo-all-trans retinoic acid, 4-oxo-13-cis-retinoic acid and retinol binding protein concentrations	X	X
Serum creatinine, BUN, ALT, bilirubin, albumin	X	X
Urine creatinine and pH	X	X

4.3.4. Dextromethorphan administration: Following a ≥ 4 hour fast, subjects will receive DM (alcohol free) 30 mg orally on each study day. DM was selected as our CYP2D6 probe because it is a standard probe for CYP2D6 activity and has a well-established safety record in adolescent patients and children.(4,131-134)

4.3.5. Isotretinoin administration: Isotretinoin administration will follow routine clinical practice. Isotretinoin administration will not be altered for research purposes. The Phase 2 study with concomitant isotretinoin will take place once patients have been taking oral isotretinoin 1 mg/kg/day for ≥ 1 week. If the patient does not tolerate 1 mg/kg/day and is reduced to 0.5 mg/kg/day as their final isotretinoin dose, then ≥ 1 week after starting that dose, subjects will complete their Phase 2 study. Subjects receiving higher doses will also be included. We will attempt to study all subjects while receiving ~ 1 mg/kg/day, but recognize that some patients might require higher or lower doses and will be studied on their clinically indicated dose.

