Effects of Isotretinoin on CYP2D6 Activity

NCT03076021

3/6/2017

Dextromethorphan/dextrorphan metabolic ratio: All urine will be collected over 4 hours following DM administration for measurement of our endpoint, urinary DM/DX MR, as previously described. Urine pH will also be measured. We recognize that urinary DM/DX MR is influenced by renal clearance (blood flow, secretion and filtration), changes in CYP3A activity or changes in urine pH. Urine samples will be analyzed for DM, DX, 3-methoxymorphinan, 3-hydroxymorphinan and DX-O-glucuronide concentrations using our validated UHPLC-MS/MS assay.

CYP2D6 genotype: Buccal swabs will be collected from each subject for CYP2D6 genotyping prior to the first DM study. The following CYP2D6 genotypes will be determined: *CYP2D6*3* (2549delA), *CYP2D6*4* (1846G>A), *CYP2D6*5* (*CYP2D6* deleted), *CYP2D6*6* (1707delT), *CYP2D6*9* (2613 delAGA), *CYP2D6*10* (100C>T), *CYP2D6*17* (1023C>T), *CYP2D6*35* (-1584 C>G and 31G>A) and *CYP2D6*41* (2988 G>A) as previously described using commercially available TaqMan assays. The genotype will be used to predict the subject phenotype (PM, IM, EM or UM) as well as activity scores (0, 0.5, 1, 1.5, 2 and 3) as described previously. Only extensive metabolizers with index scores based on genotype of 1, 1.5 and 2 will proceed with the DM portion of the study.

DX/DM MRs were calculated by dividing the molar quantity (urine) of the metabolite by that of the parent. DX plus DX-O-glucuronide/DM urinary MR was calculated by dividing the sum of the molar quantity of metabolites by that of the parent. Urine samples with concentrations above or within 5% of the LLOQ were accepted, and concentrations lower than that were excluded from data analysis. DX/DM and DX plus DX-O-glucuronide/DM MRs were analyzed only in CYP2D6 EMs (AS = 1-2). The GMR and 90% CI were used to compare urinary MRs between study timepoint 1 (pre-treatment control) and study timepoint 2 (with isotretinoin treatment). The 90% CI of the GMR for the MR with isotretinoin treatment over pre-treatment control was compared to the bioequivalence range of 0.8 and 1.25 according to FDA Guidance of Clinical Drug Interaction Studies. If the 90% CI does not include 1, there is an indication of a potential drug interaction. Statistical analyses were all conducted on GraphPad Prism 9.5.1 (GraphPad Software, Inc., La Jolla, CA, USA).

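### Does the SAP need a planned analysis of the plasma retinoids that are measured in both phases?

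*Protocol*

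**What the plan says.** The Background of the Protocol puts forward a hypothesis about retinoic acid concentrations and liver retinoid signalling as regulators of CYP2D6, "which in turn contributes to inter-individual pharmacokinetic variability of CYP2D6 substrates". It predicts a direction: "Higher retinoic acid concentrations should lead to lower CYP2D6 activity". It later says the study will assess isotretinoin's effect on the enzyme and "simultaneously directly test the hypothesis that retinoids play a role in CYP2D6 regulation in humans". The summary paragraph just before the Objective adds that "exploring the relationship between CYP2D6 activity and retinoid concentrations in humans will provide mechanistic understanding of the variability in drug therapy", and links this to a possible endogenous biomarker.

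The Objective itself is narrower. It asks only whether isotretinoin administration reduces CYP2D6 activity in adolescents.

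The table in Protocol 4.3.3 marks the following for both phases: "Total plasma all-trans retinoic acid, 13-cis-retinoic acid, retinol (all-trans and 13-cis), retinyl palmitate, 4-oxo-all-trans retinoic acid, 4-oxo-13-cis-retinoic acid and retinol binding protein concentrations". It gives no purpose for the panel. Protocol 4.3.5 leaves the isotretinoin dose to routine care, with the remark "We will attempt to study all subjects while receiving ~ 1 mg/kg/day".

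The SAP covers urine collection and assay, genotyping, calculation of two urinary ratios, a quantification-limit rule for urine, and one type of comparison: "The GMR and 90% CI were used to compare urinary MRs between study timepoint 1 (pre-treatment control) and study timepoint 2 (with isotretinoin treatment)". The interval is read against 0.8 to 1.25 and against 1. Plasma retinoids and retinol binding protein do not appear.

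**The concern.** Blood is drawn for a retinoid panel in both phases, the Background speaks of relating concentrations to activity, and the SAP is silent on how that would be done. A GMR averages over subjects, so it cannot show whether those with larger rises in retinoic acid had larger falls in activity.

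Two things would be at stake. The between-subject side of the scientific rationale would have no planned answer. And if the retinoid data were examined later without a plan, the analyte and the urinary ratio could be picked after seeing which gave the most striking result.

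**Working it through.** **Is the gap real?** Yes. The retinoid measures appear in the Protocol 4.3.3 schedule and nowhere in the SAP, not even as a descriptive summary.

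**What the GMR cannot see.** Take four hypothetical subjects with rises in log retinoic acid of x = 1.0, 1.5, 2.0 and 2.5 (mean 1.75).

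- Slope 0: each individual ratio is 0.70, so the GMR is 0.70.
- Slope −0.3: ratio = exp[ln 0.70 − 0.3(x − 1.75)], giving 0.877, 0.755, 0.649 and 0.559. Their geometric mean is again 0.70.

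The planned comparison cannot separate the two patterns. In both, however, it gives the right answer to the Objective: average activity fell by 30%.

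**Which question is the plan committed to?** Set the statements side by side.

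- The Background says the hypothesis will be tested directly by measuring CYP2D6 activity before isotretinoin and during it. That is the SAP's GMR.
- The remark about testing the retinoid hypothesis simultaneously fits the same reading: giving a retinoid and comparing activity before and during serves both purposes at once. It need not promise a second test.
- Inter-individual variability is presented as a consequence of the hypothesis, and biomarker work as further research if the hypothesis holds.
- The Objective lists no concentration-response aim.

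That the panel was scheduled to study the concentration-activity relation is therefore a reasonable inference, not a stated aim.

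**How large is the selection risk?** Measures: all-trans and 13-cis retinoic acid, all-trans and 13-cis retinol, retinyl palmitate, two 4-oxo metabolites and retinol binding protein = 8. With the SAP's two ratios, 8 × 2 = 16 regressions. Chance of at least one p<0.05 under no relation:

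| Assumption | 8 regressions (one ratio) | 16 regressions (both ratios) |
|---|---|---|
| All independent | 1 − 0.95^8 = 34% | 1 − 0.95^16 = 56% |
| Analytes correlated 0.5, ratios 0.9 (simulated, n = 12 to 20) | about 26% | about 35% |
| Analytes correlated 0.8, ratios 0.9 (simulated, n = 12 to 20) | about 17% | about 23% |

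The correlations are assumptions. Independence is not realistic: both ratios share dextrorphan and dextromethorphan, and the analytes are isomers, metabolites and a carrier protein.

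**What would a planned slope deliver?** Neither document gives a sample size. For an assumed observed correlation of 0.5, the 95% CI is tanh(atanh 0.5 ± 1.96/√(n − 3)):

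- n = 12: −0.10 to 0.83
- n = 20: 0.07 to 0.77
- n = 30: 0.17 to 0.73

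With about 1 mg/kg/day sought for everyone, exposure may vary little, which would widen the interval for the slope. Because dose follows clinical need, the slope would also be observational. A null slope would not refute the mechanism.

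**Is there one obvious analysis to prescribe?** No.

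- Regressing the within-subject change in log ratio on the change in log retinoic acid addresses the drug-induced rise, but it differences out baseline levels. The endogenous-biomarker idea in the Background points instead to Phase 1 activity against Phase 1 retinoids across subjects, allowing for activity score.
- The analyte is open too. 13-cis-retinoic acid is the compound given, but the animal evidence the Background cites is for all-trans-retinoic acid.
- Adjusting for time since the last isotretinoin dose would need a data item that neither document mentions.

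**The case for a change.** The strongest case for acting runs as follows. The hypothesis is worded in terms of concentrations and makes a directional prediction about them. Adolescents give blood for a full panel at both visits. One average ratio cannot speak to variation between subjects, and a sentence in the SAP naming one analyte and one ratio would cost almost nothing while removing the freedom to choose afterwards. If the panel is only there to confirm exposure, the SAP could say so.

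Much of this stands. The SAP is silent, the GMR is blind to a concentration gradient, and naming a measure in advance is better practice than choosing one later. What does not stand is the step from there to a needed change. The gradient is not in the Objective, the selection risk belongs to analyses nobody has proposed, and the obvious remedy would leave the endogenous relation unanalysed. The SAP's statistical paragraph is also written in the past tense. If the data have already been examined, a new analysis could no longer be called prespecified, only post hoc.

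**Conclusion.** No change to the plan is needed. The SAP has a gap in exploratory detail, not a flaw in what it sets out to show. Followed as written, it answers the formal Objective with the comparison that the Background names as the test, and no planned estimate, interval or conclusion would alter if a retinoid analysis were added.

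The 34% and 56% figures are upper illustrations under independence. Under the correlations assumed above they fall to between 17% and 35%, and they apply only if such regressions were run and the best one picked.

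Analysts holding these measurements would be expected to look at them. Sensible practice is to label that work exploratory (or post hoc if the data have been seen), give a reason for the retinoid measure chosen, and report slopes with intervals. This conclusion rests on reading the Objective, not the Background's wider rationale, as what the study commits to. It would be different if a report presented a retinoid-activity correlation as a confirmed finding.

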Effects of Isotretinoin on CYP2D6 Activity

NCT03076021

3/6/2017

Dextromethorphan/dextrorphan metabolic ratio: All urine will be collected over 4 hours following DM administration for measurement of our endpoint, urinary DM/DX MR, as previously described. Urine pH will also be measured. We recognize that urinary DM/DX MR is influenced by renal clearance (blood flow, secretion and filtration), changes in CYP3A activity or changes in urine pH. Urine samples will be analyzed for DM, DX, 3-methoxymorphinan, 3-hydroxymorphinan and DX-O-glucuronide concentrations using our validated UHPLC-MS/MS assay.

CYP2D6 genotype: Buccal swabs will be collected from each subject for CYP2D6 genotyping prior to the first DM study. The following CYP2D6 genotypes will be determined: *CYP2D6*3* (2549delA), *CYP2D6*4* (1846G>A), *CYP2D6*5* (*CYP2D6* deleted), *CYP2D6*6* (1707delT), *CYP2D6*9* (2613 delAGA), *CYP2D6*10* (100C>T), *CYP2D6*17* (1023C>T), *CYP2D6*35* (-1584 C>G and 31G>A) and *CYP2D6*41* (2988 G>A) as previously described using commercially available TaqMan assays. The genotype will be used to predict the subject phenotype (PM, IM, EM or UM) as well as activity scores (0, 0.5, 1, 1.5, 2 and 3) as described previously. Only extensive metabolizers with index scores based on genotype of 1, 1.5 and 2 will proceed with the DM portion of the study.

DX/DM MRs were calculated by dividing the molar quantity (urine) of the metabolite by that of the parent. DX plus DX-O-glucuronide/DM urinary MR was calculated by dividing the sum of the molar quantity of metabolites by that of the parent. Urine samples with concentrations above or within 5% of the LLOQ were accepted, and concentrations lower than that were excluded from data analysis. DX/DM and DX plus DX-O-glucuronide/DM MRs were analyzed only in CYP2D6 EMs (AS = 1-2). The GMR and 90% CI were used to compare urinary MRs between study timepoint 1 (pre-treatment control) and study timepoint 2 (with isotretinoin treatment). The 90% CI of the GMR for the MR with isotretinoin treatment over pre-treatment control was compared to the bioequivalence range of 0.8 and 1.25 according to FDA Guidance of Clinical Drug Interaction Studies. If the 90% CI does not include 1, there is an indication of a potential drug interaction. Statistical analyses were all conducted on GraphPad Prism 9.5.1 (GraphPad Software, Inc., La Jolla, CA, USA).

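### Does analysing two urinary ratios against one named endpoint leave the interaction rule undefined?

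*SAP*

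**What the plan says.** The SAP's opening paragraph, on the dextromethorphan/dextrorphan metabolic ratio, describes the urine collection as serving "measurement of our endpoint, urinary DM/DX MR, as previously described". Only one endpoint is named. The table in Protocol 4.3.3 agrees: its only metabolic-ratio row is "4-hour urinary DM/DX MR", marked for both phases.

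The SAP's final paragraph turns the ratio over: "DX/DM MRs were calculated by dividing the molar quantity (urine) of the metabolite by that of the parent". It adds a second quantity: "DX plus DX-O-glucuronide/DM urinary MR was calculated by dividing the sum of the molar quantity of metabolites by that of the parent". Both are carried into the analysis: "DX/DM and DX plus DX-O-glucuronide/DM MRs were analyzed only in CYP2D6 EMs (AS = 1-2". The comparison is stated in the plural: "The GMR and 90% CI were used to compare urinary MRs between study timepoint 1 (pre-treatment control) and study timepoint 2". The next two sentences return to the singular, setting one interval against 0.8 to 1.25 and then giving the rule: "If the 90% CI does not include 1, there is an indication of a potential drug interaction".

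Neither document labels a ratio primary or supportive, or says what to conclude if only one interval excludes 1.

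**The concern.** The plan has one objective, whether isotretinoin lowers CYP2D6 activity, and one rule for answering it. A rule needs a named input. Two ratios are available and only one can be the named endpoint inverted. The other differs by the amount of conjugated dextrorphan, so the two can move apart if conjugation changes between phases.

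Two things would be at stake. First, if one 90% CI excluded 1 and the other did not, a reader could ask which result is the trial's answer. Second, if either ratio were allowed to trigger the rule, the chance of a false signal would exceed the 10% that goes with a single 90% CI. The SAP's analysis text is in the past tense, so there is also the question of whether the deciding ratio was fixed before the results were seen.

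**Working it through.** The documents give no sample size, SD, power or alpha for this comparison, so there is no planned figure to reproduce.

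**1. Does turning DM/DX into DX/DM matter?** On the log scale, inversion changes the sign of every within-subject difference. The GMR becomes 1/GMR, and limits (L, U) become (1/U, 1/L). An interval that excludes 1 still excludes it. The reference range maps onto itself: 1/0.8 = 1.25 and 1/1.25 = 0.8. A simulated paired example gave a GMR of 0.919 (0.838 to 1.007) one way up and 1.089 (0.993 to 1.193) the other, with the same decision. Only the direction of reading changes: lower CYP2D6 activity raises DM/DX and lowers DX/DM.

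**2. Is the second ratio a relabelling?** No. Writing DXG for DX-O-glucuronide,

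(DX + DXG)/DM = (DX/DM) × (1 + DXG/DX).

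The two GMRs agree only if the conjugated share is stable. Suppose the summed ratio is unchanged (GMR 1.0). With assumed conjugated shares, a move from 95% to 97% gives a free-ratio GMR of 0.03/0.05 = 0.60, and a move from 95% to 94% gives 0.06/0.05 = 1.20. The shares are illustrations, not figures from the documents.

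**3. What would follow if either ratio could trigger the rule?** A 90% CI excluding 1 is a two-sided test at 0.10 with critical value 1.645. For two ratios with correlation ρ between their standardised estimates (bivariate normal):

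- P(either excludes 1) = 1 − P(both |Z| < 1.645)
- P(both exclude 1) = 0.20 − P(either), with no true effect
- P(exactly one excludes 1) = P(either) − P(both)

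The last column repeats the third quantity for equal true effects that give each ratio 50% power.

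| ρ (assumed) | Either, no effect | Exactly one, no effect | Exactly one, 50% power each |
|---|---|---|---|
| 0 | 0.1900 | 0.1800 | 0.500 |
| 0.5 | 0.1755 | 0.1510 | 0.334 |
| 0.8 | 0.1505 | 0.1010 | 0.206 |
| 0.9 | 0.1363 | 0.0725 | 0.144 |
| 0.95 | 0.1258 | 0.0517 | 0.102 |
| 0.99 | 0.1116 | 0.0232 | 0.045 |

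At ρ = 0 the false-positive rate is 1 − 0.90² = 0.19; at ρ = 1 it is 0.10. The documents do not give ρ. The shared denominator DM makes it probably positive. Sharing DX adds to it only if free DX is a material part of the summed metabolite, which the documents do not say. The full range is therefore the fair statement.

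**4. Does the SAP state an either-ratio rule?** The decision sentences are singular. The one plural is in the comparison sentence, and the same paragraph also uses a plural for a single type of ratio when it defines DX/DM. The plural can therefore refer to subjects or timepoints. Set beside a singular named endpoint in both documents, the singular rule attaches most naturally to that endpoint. On that reading the two-sided false-positive rate is 0.10, or 0.05 in the hypothesised direction.

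**The case for a change.** The best case for a change is that the analysis paragraph treats both ratios alike, never refers back to the endpoint, and leaves the input to its only decision rule for the reader to infer. Writing one line would cost nothing. It would also settle what DX means: the endpoint is measured by a method described in a source not reproduced here, so free versus total dextrorphan cannot be settled from the documents. If total dextrorphan were meant, the glucuronide-inclusive ratio would be the named endpoint inverted.

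Part of this stands. The gap in wording is real, the second ratio is a different quantity, and the probabilities above are arithmetically correct. The SAP does list DX and DX-O-glucuronide as separate analytes and as separate terms in the second ratio, which favours free DX without proving it.

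What does not stand is the step from silence to a wrong result. The error inflation needs a rule the SAP does not contain. The chance of disagreement depends on a correlation and on power that the documents do not give: at 50% power each it runs from 4.5% at correlation 0.99 to 50% at correlation 0. The SAP's conclusion is also worded as an indication of a potential interaction, in a study the Protocol's Background presents as a first step, so strict multiplicity control is partly a matter of preference.

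**Conclusion.** No change to the plan is called for. The SAP leaves out a detail that an analyst would fill sensibly: the rule belongs to the single named endpoint, expressed as DX/DM, and the glucuronide-inclusive ratio is additional. Reversing the ratio is a labelling inconsistency and changes neither the exclusion of 1 nor the comparison with 0.8 to 1.25. No rule as stated gives a wrong answer, and because both ratios are analysed, reporting both GMRs with their 90% CIs would show any disagreement.

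The false-positive rate is 10% two-sided on the natural reading. It would be between 10% and 19% only under an either-ratio rule that the SAP does not state. The conclusion rests on DX meaning free dextrorphan, which the separate analyte list supports, and on both ratios being reported. A reader of the results should check that both appear, which way up they are expressed, and, if they disagree, when the deciding one was chosen.

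### 3-methoxymorphinan and 3-hydroxymorphinan are assayed but enter no analysis, so an isotretinoin effect on the CYP3A route could not be told apart from an effect on CYP2D6

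*SAP*

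**What the plan says.** The SAP paragraph on the dextromethorphan/dextrorphan metabolic ratio (MR) names the endpoint: "All urine will be collected over 4 hours following DM administration for measurement of our endpoint, urinary DM/DX MR". The Protocol's Study Design Summary (4.3.3) lists the same measure, "4-hour urinary DM/DX MR", and no separate measure of CYP3A activity.

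The same SAP paragraph lists five urinary analytes: "Urine samples will be analyzed for DM, DX, 3-methoxymorphinan, 3-hydroxymorphinan and DX-O-glucuronide concentrations using our validated UHPLC-MS/MS assay". It also recognises that the MR is "influenced by renal clearance (blood flow, secretion and filtration), changes in CYP3A activity or changes in urine pH".

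The SAP's final paragraph defines what is analysed:
- The first ratio, DX/DM, takes moles of DX over moles of DM in the urine.
- The second adds the glucuronide to the numerator: "DX plus DX-O-glucuronide/DM urinary MR was calculated by dividing the sum of the molar quantity of metabolites by that of the parent"

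Each is compared between the two timepoints by a GMR with a 90% CI. The CI is set against 0.8 to 1.25, and a CI that excludes 1 is taken as a sign of a possible interaction. The Protocol's Objective concerns CYP2D6 specifically.

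**The concern.** Take O-demethylation as the CYP2D6 step and N-demethylation as the CYP3A step; this is an assumption, since the documents do not set out the pathway. DX that is N-demethylated leaves the numerator of both planned ratios and appears as 3-HM. If that step speeds up, both ratios fall; if it slows, both rise. CYP2D6 need not have changed in either case.

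A CYP3A change caused by isotretinoin would be present only at the second timepoint. Using subjects as their own controls does not remove it, and neither does a larger sample. The SAP names this influence and assays the two analytes that could reveal it, but gives no rule for using them. At stake is whether a shift in the MR can be read as an answer to the CYP2D6 question.

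**Working it through.** **1. Analytes set against ratios.**

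| Analyte | Assayed | DX/DM | (DX + DX-O-glucuronide)/DM |
|---|---|---|---|
| DM | yes | yes | yes |
| DX | yes | yes | yes |
| DX-O-glucuronide | yes | no | yes |
| 3-MM | yes | no | no |
| 3-HM | yes | no | no |

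The named endpoint, DM/DX, is the inverse of the first ratio and adds nothing on this point. The plan gives no sample size, SD or effect size, so there is no figure to reproduce. Everything below is illustrative.

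**2. Closed form, complete collection.** Let f be the share of DX that goes on to 3-HM, and let CYP3A activity change c-fold with CYP2D6 unchanged. Total urinary (DX + DX-O-glucuronide)/DM equals (O-demethylation constant / DM renal constant) × (1 − f). N-demethylation of DM itself cancels. The new value of 1 − f is (1 − f)/(1 − f + cf), so both planned ratios change by

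GMR = 1/(1 − f + cf).

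| f (assumed) | CYP3A doubled | CYP3A halved | CYP2D6 down 30% and CYP3A halved |
|---|---|---|---|
| 2% | 1/1.02 = 0.98 | 1/0.99 = 1.01 | 0.7/0.99 = 0.71 |
| 10% | 1/1.10 = 0.91 | 1/0.95 = 1.05 | 0.7/0.95 = 0.74 |
| 20% | 1/1.20 = 0.83 | 1/0.90 = 1.11 | 0.7/0.90 = 0.78 |
| 30% | 1/1.30 = 0.77 | 1/0.85 = 1.18 | 0.7/0.85 = 0.82 |

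In the last row a true 30% fall moves back inside 0.8 to 1.25.

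**3. Four-hour urine.** A linear model was integrated to 4 hours. Its assumed constants per hour are:
- absorption 1.0
- DM: O-demethylation 2.0, N-demethylation 0.1 or 0.3, renal 0.05
- DX: glucuronidation 2.0, N-demethylation 0.05, 0.3 or 1.0, renal 0.1
- DX-O-glucuronide: renal 0.4
- 3-MM: O-demethylation 1.0, renal 0.1
- 3-HM: renal 0.4

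Here f = 0.05/2.15 = 2.3%, 0.3/2.4 = 12.5% or 1.0/3.1 = 32%. Ranges are over the two DM N-demethylation values.

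CYP3A doubled, CYP2D6 unchanged:

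| f | DX/DM | (DX + DX-O-glucuronide)/DM | 3-HM/(DX + DX-O-glucuronide) | 3-MM/DM |
|---|---|---|---|---|
| 2.3% | 0.979–0.980 | 0.985–0.992 | 2.03–2.04 | 2.00–2.01 |
| 12.5% | 0.893–0.894 | 0.906–0.911 | 2.05–2.11 | 2.00–2.01 |
| 32% | 0.760–0.761 | 0.776–0.781 | 2.07–2.16 | 2.00–2.01 |

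CYP2D6 down 30%, CYP3A unchanged:

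| f | DX/DM | (DX + DX-O-glucuronide)/DM | 3-HM/(DX + DX-O-glucuronide) | 3-MM/DM |
|---|---|---|---|---|
| 2.3% | 0.694–0.695 | 0.670–0.675 | 1.13–1.17 | 1.25 |
| 12.5% | 0.695–0.696 | 0.671–0.676 | 1.05–1.10 | 1.25 |
| 32% | 0.696–0.697 | 0.672–0.677 | 1.02–1.05 | 1.25 |

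The 3-HM column follows from the others. At f = 2.3%, DX/3-HM changes by 0.920, DX/DM by 0.694 and (DX + DX-O-glucuronide)/DM by 0.670, so the check changes by (1/0.920) × (0.694/0.670) = 1.13. Other sets of constants gave 1.00 to 1.12 for this ratio and about 1.1 to 1.4 for 3-MM/DM. The 3-HM ratio therefore separates the two explanations better.

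**4. Effect on the decision rule.** Assume 20 pairs and a within-subject log SD s, so SE = s√(2/20). At f = 20% the 4-hour spurious GMR with CYP3A doubled is about 0.85, and ln 0.85 = −0.1625. For s = 0.2, 0.3 and 0.4, SE = 0.063, 0.095 and 0.126. The noncentral t then gives a 90% CI excluding 1 in 80%, 50% and 34% of trials, against a nominal 10%. For a spurious GMR of 0.98 the figures are 12%, 11% and 10%.

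**The case against.** - **No CYP3A effect is shown.** Nothing in the documents says that isotretinoin alters CYP3A. A reader might infer that the planned result is biased; the documents support only that it could be. This stands.
- **The size is assumed.** f, c, the rate constants, the number of pairs and the SD all come from outside the documents. At f of about 2% the bias is negligible. This stands, and is why a range is given.
- **The SAP does not assign the effect to an enzyme.** A reader might infer that any shift will be attributed to CYP2D6. The SAP's wording is tentative, speaks only of a possible interaction, and openly names CYP3A as an influence. No attribution rule is written. What remains is that the objective is CYP2D6-specific and nothing planned separates the two explanations.
- **Descriptive reporting is not barred.** True, but an analysis chosen after the results are seen carries less weight than one stated beforehand.
- **A single combined ratio looks like a cure.** (DX + DX-O-glucuronide + 3-HM)/(DM + 3-MM) is independent of CYP3A only if DM and 3-MM share O-demethylation and renal constants, recovery is near complete, and no 3-HM conjugate goes unmeasured. The documents establish none of these. With CYP3A doubled and CYP2D6 unchanged, it stayed at 0.99 to 1.02 under favourable constants. It fell to 0.84–0.93 with the constants above, and to 0.75 in a variant with 3-MM renal clearance five times higher. It can move the same way as the planned ratios and so appear to confirm a false CYP2D6 effect. This objection stands.
- **The checks also respond to CYP2D6.** True of 3-MM/DM, and slightly of 3-HM/(DX + DX-O-glucuronide), mostly when f is small. In that region the bias is itself small.

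**Conclusion.** The concern holds as a gap in the analysis, not as a demonstrated bias. The plan acknowledges a CYP3A influence, assays two analytes that bear on it, and uses neither. If isotretinoin changed CYP3A, the planned ratios could not distinguish that from a CYP2D6 effect. On the assumed pathway, doubling CYP3A with CYP2D6 unchanged gives a GMR from about 0.98–0.99 (f about 2%) to about 0.77–0.79 (f about 30%), that is, from negligible to decisive. Halving CYP3A could hide part of a true fall. The separate ratio 3-HM/(DX + DX-O-glucuronide) roughly doubled in every scenario with CYP3A doubled, and moved at most 1.17-fold at 4 hours for a 30% CYP2D6 fall. The change is worth making because it affects what the trial can conclude. Confidence is moderate, since every magnitude rests on inputs that the documents do not give.

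**What to change.** Keep both planned ratios and add the following to the SAP's final paragraph, in the same subjects.

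1. **Main N-demethylation check:** GMR and 90% CI for 3-HM/(DX + DX-O-glucuronide).
2. **Secondary check:** GMR and 90% CI for 3-MM/DM, with a note that it also rises when CYP2D6 falls (about 1.1 to 1.4-fold for a 30% fall in the models).
3. **Reading rule:** attribute a shift in the planned ratios to CYP2D6 without qualification only if the check shows no material change. If it moves, report the result as not specific to CYP2D6. Define material change beforehand and judge it on the interval, not on a non-significant result. One option is the SAP's own 0.8 to 1.25. If the check tracks CYP3A, then at f = 30% that leaves a bias between 1/(0.7 + 1.25 × 0.3) = 0.93 and 1/(0.7 + 0.8 × 0.3) = 1.06.
4. **Combined ratio:** exploratory at most, never the condition for attributing an effect to CYP2D6.

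The cost is three short extra analyses of concentrations already assayed, with no new samples, visits or assays. Some 3-MM or 3-HM values may fall below the LLOQ and be excluded under the SAP's existing rule, so the number of pairs behind each check should be reported. If that leaves the check's interval wide, the qualification remains.
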